# 4.2.2 Safety

Complications identified in the four clinical publications are reported in Table 4.2.2 -1.

Author, Year	# of	Perforation	Hematoma	Edema (n)	Inflammation	Infection
	Pts	(n)	(n)		(n)	(n)
Sainio12,2019	101	1	1	-	-	6
Sowerby⁵, 2013	8	1	-	2	-	-
Tami  , 2010	24	-	-	-	5	-
Yildirim  , 2013	20*	-	-	-	-	-
Total	153	2	1	2	5	6

Table 4.2.2-1. ENTACT Septal Stapler Complications

# \*Estimated number of patients

Device related complications were reported in three studies. Perforation was reported in two studies. Sainio et al. reported perforation in 1 patient (0.99%) in the ENTACT Stapler group and a reoperation was performed in this patient. Sowerby et al. reported a 1 mm postoperative perforation occurred in one patient (12.5%) due to jamming of the ENTACT Septal Stapler (2009) and stated that this can be avoided with the newer model (2010/2012) of the stapler. Perforation was in line with other outcomes reported in the State of the Art for alternative

### CONFIDENTIAL AND PROPRIETARY

Study Protocol	% smith&nephew
A prospective, multi-center, single arm PMCF study to evaluate the safety and performance of ENTACT™ (Next Generation) resorbable septal staple system for septoplasty	Number: ENTACT.ENT.PRO.SEP.2019.05
	Version: 2.0, 27Aug2020 Page: Page 24 of 94

devices for the Sainio study. In Sowerby et al., the authors concluded that the septal stapler can be used without an increased morbidity in comparison to suture closure or impact to subjective patient scores.

Tami et al. reported that the first lot of ENTACT Septal Staplers (2009) failed to perform to design specifications and only four total staples from three staplers were implanted in one patient.

Sainio et al. observed haematoma in one patient in the ENTACT Stapler group. Sainio et al. reported that perforation and haematoma, which occurred at a low rate of 1% each in the study, is in agreement with the study conducted by Tami et al. and stated that "ENTACT Septal Stapler is safe to use". The complications reported in the four studies of the ENTACT stapler are performing in-line with alternative devices on the market as discussed in the State of the Art.

Some of the minor complications observed in the literature were edema, inflammation and infection. Sowerby et al. conducted a prospective, randomized clinical study comparing ENTACT Septal Stapler to quilting sutures in patients undergoing septoplasty. Sowerby et al observed mild edema in 2 patients in both the groups at a 3 week follow up. However, the edema resolved in 2 months. In a prospective, case series, mild inflammation was reported at a 1 week follow up in 21% of the patients in whom ENTACT Septal Stapler was used for approximation of mucoperichondrial flaps after septoplasty whereas no inflammation was observed in 79% of the patients. Expected rates of edema or inflammation following septoplasty were not discussed in the four publications identified. Other complications reported in the literature include bleeding, and fever.

Sainio et al. conducted a retrospective comparative study comparing ENTACT Septal Stapler to the non-stapler group where silicone splints, tamponade, or sutures were used during septoplasty. No significant difference in the complication rate was observed between the

This document contains information that is confidential and proprietary to Smith + Nephew PLC and Smith + Nephew, Inc. and is intended for use only by Smith + Nephew and its manufacturer. It shall not be reproduced or copied in whole or in part, nor shall the contents be disclosed by any means without prior written permission from Smith + Nephew, nor shall anyone make any use of it that is contrary to the expressed or implied wishes of Smith + Nephew.

Study Protocol	> ∕ smith&nephew
A prospective, multi-center, single arm PMCF study to evaluate the safety and performance of ENTACT™ (Next Generation) resorbable septal staple system for septoplasty	Number: ENTACT.ENT.PRO.SEP.2019.05
	Version: 2.0, 27Aug2020
	Page: Page 25 of 94

ENTACT Septal Stapler group (9.9%) and the subgroups such as silicone splint group (9.7%), suture group (12.7%), and the tamponade group (9.5%) in the non-stapler group.

Since the ENTACT (Next Generation) Septal Stapler utilizes the same staples and a similar delivery mechanism to the previous ENTACT Septal Stapler, it is anticipated that the Next Generation device will perform the same as the previous generation device.

# 4.3 **STUDY PURPOSE**

To provide evidence to satisfy the PMCF requirements of Conformité Européene (CE) marking to market this device in Europe (data may be used to support registrations on other countries as well).

# 4.4 SAFETY CONSIDERATIONS

The ENTACT Septal Stapler delivers implantable septal staples that are intended to connect internal tissues to aid healing and for approximation of soft tissue during nasal surgery. Representative language of the contraindications and potential adverse effects from the ENTACT Septal Stapler can be found in the instructions for use (IFU). The ENTACT Septal Stapler are supplied sterile. The ENTACT stapler is sterilized using Gamma Irradiation.

Potential Adverse Effects listed in the IFU include:

- Possible adverse effects include but are not limited to wound complications, including hematoma, site drainage, infection, toxic shock syndrome, and other complications that are possible with any surgery.
- When implanted, the ENTACT Staple may elicit a minimal tissue reaction characteristic of foreign body response to a substance. The tissue reaction resolves as the material is absorbed.

This document contains information that is confidential and proprietary to Smith + Nephew PLC and Smith + Nephew, Inc. and is intended for use only by Smith + Nephew and its manufacturer. It shall not be reproduced or copied in whole or in part, nor shall the contents be disclosed by any means without prior written permission from Smith + Nephew, nor shall anyone make any use of it that is contrary to the expressed or implied wishes of Smith + Nephew.

Study Protocol	% smith&nephew
A prospective, multi-center, single arm PMCF study to evaluate the safety and performance of ENTACT™ (Next Generation) resorbable septal staple system for septoplasty	Number: ENTACT.ENT.PRO.SEP.2019.05
	Version: 2.0, 27Aug2020

• Fracture or extrusion of the ENTACT Staple, with or without generation of particulate debris.

# 4.4.1 Tolerance limits for potential adverse effects derived from literature

Based on the state of the art data in **Table 4.2.2-1** and **Section 4.2.2** the expected tolerance limits for potential adverse effects from literature in the ENTACT Septal Stapler system are stated in **Table 4.4.1-1**.

Expected Complications	Tolerance limits	Tolerance limits to show no significant
(derived from literature)	from literature	difference from literature* (maximum
		allowed)
Perforation	2/153 (1.31%)	2/40 5% (95% CI 0.6% to 16.92%)
Hematoma	1/153 (0.65%)	2/40 5% (95% CI 0.6% to 16.92%)
Edema	2/153 (1.31%)	2/40 5% (95% CI 0.6% to 16.92%)
Inflammation	5/153 (3.27%)	4/40 10% (95% CI 2.8% to 23.7%)
Infection	6/153 (3.92%)	4/40 10% (95% CI 2.8% to 23.7%)

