# Table 4.4.1-1. ENTACT Septal Stapler Tolerance Limits

\* These numbers have been derived based on the study sample size of N=40.

Actual study adverse events occurrences will be reviewed under **Section 10.5 and Section 12** and assessed relative to the tolerance limits.

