# Figure 6.1.3-1 Distal head changes from current device (top) to new device (bottom)

- Biological
  - Counter tension arm - There are no impact of differences in material for the counter tension arm as PARA has mechanical properties close to stainless steel, and is commonly used in medical devices. Smith+Nephew has conducted both biological and mechanical testing, and has objective evidence that the new device meets all the same requirements as the current device.
  - Pins in Channel - There are no impact of differences in material for the pins in channel as 18-8 stainless steel are in the 300 series stainless steel family, with different naming conventions. These designations are considered interchangeable as 300 Series stainless steels are required to contain 18% chromium and 8% nickel and 18-8 means the steel is 18% chromium and 8% nickel. Smith+Nephew has conducted both biological and mechanical testing, and has objective evidence that the new device meets all the same requirements as the current device.

This document contains information that is confidential and proprietary to Smith + Nephew PLC and Smith + Nephew, Inc. and is intended for use only by Smith + Nephew and its manufacturer. It shall not be reproduced or copied in whole or in part, nor shall the contents be disclosed by any means without prior written permission from Smith + Nephew, nor shall anyone make any use of it that is contrary to the expressed or implied wishes of Smith + Nephew.

Study Protocol	>∕; smith&nephew
A prospective, multi-center, single arm PMCF study to evaluate the safety and performance of ENTACT™ (Next Generation) resorbable septal staple system for septoplasty	Number: ENTACT.ENT.PRO.SEP.2019.05 Version: 2.0, 27Aug2020
	Page: Page 34 of 94

The minor differences between the comparable device previous generation ENTACT Septal Stapler and Next Generation ENTACT Septal Stapler, are expected to have no impact to the safety of the devices. As these devices as considered comparable, we expect similar clinical safety and performance outcomes.

Refer to the ENTACT Septal Stapler Instructions for Use for more information.

- Do NOT place a staple where the needle path is obstructed or a collision with any object may occur.
- Do NOT use the staple on tissue which is too thick or hard (such as bone) to permit an effective tissue capture.
- Do NOT use with patients in whom radiopacity is necessary or desired since ENTACT staples are radiotransparent.

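### A count within the Table 4.4.1-1 limits shows only that no difference was detected at N=40, and cannot support a conclusion that complication rates are no higher than in the literature

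*Combined protocol and SAP*

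**What the plan says.** Section 4.4.1 states that the expected "tolerance limits for potential adverse effects from literature in the ENTACT Septal Stapler system are stated in" Table 4.4.1-1. For each complication the table gives a literature rate out of 153 patients and a maximum count out of 40 with its 95% CI. The second column is headed "Tolerance limits to show no significant" difference from the literature.

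- Perforation: 2/153 (1.31%); limit 2/40.
- Hematoma: 1/153 (0.65%); limit 2/40.
- Edema: 2/153 (1.31%); limit 2/40.
- Inflammation: 5/153 (3.27%); limit 4/40.
- Infection: 6/153 (3.92%); limit 4/40.

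The printed CIs are 0.6% to 16.92% for 2/40 and 2.8% to 23.7% for 4/40. The note under the table begins "Actual study adverse events occurrences will be reviewed under" Sections 10.5 and 12, and adds that events will be assessed relative to the limits. Neither section describes that comparison. No margin, power or acceptable excess rate is given.

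The counts come from Table 4.2.2-1 (Section 4.2.2), where a dash fills every cell without a count and has no key. For inflammation, the text says "mild inflammation was reported at a 1 week follow up in 21% of the patients in whom ENTACT Septal Stapler was used". For edema, the randomized study with 8 stapler patients "observed mild edema in 2 patients in both the groups at a 3 week follow up". The same section adds: "Expected rates of edema or inflammation following septoplasty were not discussed in the four publications identified".

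**The concern.** The column title offers a count within the limit as a showing about the device. A non-significant result in 40 patients is easy to obtain when events are rare, whether or not the device is worse. The limits are nevertheless the only numerical safety yardstick in the protocol. The study is meant as CE-marking evidence, and Section 6.1.3 already says "we expect similar clinical safety and performance outcomes". A count at or below a limit could therefore be reported as confirming comparable safety, which the data could not support.

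The edema and inflammation rows raise a separate question. Every event comes from one small study, yet the denominator is all 153 patients. If the other studies did not assess these findings, the references are too low and a device equivalent to its predecessor could breach the limits.

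**Working it through.** **Inputs.** N=40 and the literature counts are from Table 4.4.1-1; the source-study counts are from Table 4.2.2-1. Section 10.1 sets a two-sided 5% level. The Clopper-Pearson method is stated for the primary endpoint (Section 10.4.1) and is assumed here.

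**Step 1: reproduce the table.** Exact 95% CIs are 0.61% to 16.92% for 2/40 and 2.79% to 23.66% for 4/40, as printed. The lower bounds for x/40 are 0.61% (x=2), 1.57% (x=3), 2.79% (x=4) and 4.19% (x=5). The largest x whose lower bound does not exceed events/153 is 2, 2, 2, 4, 4 in table order, so all five limits match. The rule is inferred, not printed. Two alternatives do not fit: a two-sided Fisher test against events/153 would allow 3, 2, 3, 4, 5, and a one-sample exact binomial test 2, 1, 2, 3, 4.

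**Step 2: chance of staying within the limit.** With limit c and true rate p, P(X ≤ c) = Σ C(40,k) p^k (1−p)^(40−k), for k = 0 to c.

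| Complication | c | at reference | at 2× | at 3× |
|---|---|---|---|---|
| Hematoma (1/153) | 2 | 99.8% | 98.5% | 95.7% |
| Perforation (2/153) | 2 | 98.5% | 91.4% | 79.4% |
| Infection (6/153) | 4 | 98.1% | 79.8% | 48.5% |

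If the dash means not reported and only studies with a count are used (1/101, 2/109, 6/101), the 3× figures become 88%, 62% and 14%. On that reading the infection limit does detect a tripling.

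**Step 3: the best possible result.** For 0/40 the upper bound is 1 − 0.025^(1/40) = 8.8%. Divided by the references, this is 13.5 times hematoma (0.65%), 6.7 times perforation (1.31%) and 2.2 times infection (3.92%).

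**Step 4: size needed to exclude a tripling.** Assume that the true rate equals the pooled reference, and require the exact upper 95% bound to fall below three times that reference with probability at least 80%. Because the exact method is discrete, this probability moves in a sawtooth as N grows.

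| Complication | first reached at N | sustained from N | probability at N=40 |
|---|---|---|---|
| Infection | 96 | 108 | 20% |
| Perforation | 295 | 365 | 0% |
| Hematoma | 592 | 732 | 0% |

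**Step 5: edema and inflammation references.** The source-study rates are 2/8 = 25% (exact 95% CI 3.2% to 65.1%) and 5/24 = 20.8% (7.1% to 42.2%). The pooled 1.31% and 3.27% lie below both lower bounds. The chance that an equivalent device exceeds its limit is:

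| True rate assumed | Edema (more than 2/40) | Inflammation (more than 4/40) |
|---|---|---|
| pooled rate | 1.5% | 0.9% |
| lower 95% bound of source study | 13% | 15% |
| source-study rate | 99.9% | 94% |

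The wording "observed mild edema in 2 patients in both the groups at a 3 week follow up" could also mean two patients in total. With 1/8 = 12.5% (CI 0.3% to 52.7%), the edema figure is 89% instead of 99.9%, and the pooled rate no longer lies below the lower bound. The count of 2 in the stapler row of Table 4.2.2-1 favours 2/8.

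**The case against.** The strongest reply is that the column title is literally true. By the inferred rule, a count within the limit does give no significant difference, and 40 patients can readily produce that. The table does not mention equivalence and prints CIs reaching 16.92% and 23.7%, so its imprecision is visible. The 2× and 3× benchmarks are this review's choice. Section 10.5 already summarizes adverse events, Section 10.1 provides 95% CIs where appropriate, and further safety summaries are left to the SAP. All of this stands. A reader might infer that 40 patients cannot show a non-significant difference, or that the table is miscalculated; neither is so. What the reply does not answer is that these counts are the stated yardstick, under a heading that invites reading non-significance as a favourable finding.

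On the references, the dashes may be true zeros, in which case the pooled rates stand. The remark that expected rates were not discussed does not say that edema and inflammation went unassessed.

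Two further readings are tempting but not supported:

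- A reader might set the limits against the primary-endpoint item on significant local tissue reaction (Section 8.3.1) and conclude that mild findings go uncounted. The limits apply to adverse events, which Section 12.1.1 defines broadly, Section 12.1.5 grades from mild upward and Section 12.3 records whatever their kind. What stays open is only whether an investigator regards an expected mild reaction as untoward, given that Section 4.4 says "the ENTACT Staple may elicit a minimal tissue reaction characteristic of foreign body response to a substance".
- A reader might take the table as the anticipated incidence for Section 12.1.4, which refers to Section 4.4. The criterion there is the risk analysis report. Section 4.4 also carries the list of potential effects from the instructions for use, and nothing says that this table supplies an incidence.

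**Conclusion.** The concern holds as a fault of inference, not of arithmetic. A count within a limit shows that no difference was detected and cannot support a conclusion that rates are no higher than in the literature. On the pooled references, a tripling would go unflagged with probability 96% for hematoma, 79% for perforation and 49% for infection, and even zero events would not exclude it for hematoma or perforation. These figures assume 40 treated subjects, the inferred rule and the pooled /153 rates. The tripling is illustrative, because the protocol states no margin.

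The edema and inflammation point is secondary and conditional. If the dash means not reported, those references are too low and the consequence is false alarms. If it means zero, they are sound. The documents do not settle which. The two faults act in opposite directions, so the limits should not be described as uniformly lax or uniformly strict.

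**What to change.** (a) Rename the column *Count that prompts review* and delete the wording about showing no significant difference. Add to Section 10.5 or the SAP: *For each complication in Table 4.4.1-1, the number and percentage of SAF subjects with the event will be reported with an exact (Clopper-Pearson) 95% CI. A count at or below the listed count will not be reported as evidence of comparability with the literature. A higher count prompts a documented review.*

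(b) Check every dash in Table 4.2.2-1 against the cited publication, print 0 or NR (already a defined abbreviation), and use as denominator only the studies that assessed the event. Until then, show the observed edema and inflammation rates beside 2/8 (25%, 3.2% to 65.1%), noting the possible 1/8, and 5/24 (20.8%, 7.1% to 42.2%).

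Keep the current counts as review prompts. With counted-study denominators the same rule would loosen perforation to 3 (on 2/109) and infection to 6 (on 6/101), which detects less.

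Cost: one column title, one short paragraph and a check of four publications that the sponsor already cites. No new patients or data are needed. The table change is a protocol amendment needing signatory and IRB/IEC approval (Section 15). The reporting text can go in the SAP, which Section 10 says will be finalized before database lock. The price is a less favourable safety statement. Enlarging the study enough to exclude a tripling is not realistic for perforation or hematoma.

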# Table 4.4.1-1. ENTACT Septal Stapler Tolerance Limits

\* These numbers have been derived based on the study sample size of N=40.

Actual study adverse events occurrences will be reviewed under **Section 10.5 and Section 12** and assessed relative to the tolerance limits.

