# 4.2.1 Performance

Improvement in clinical outcome scores with the ENTACT Septal Stapler are reported in **Table 4.2.1-1**.

Indication	Author, Year	# of Pts	Septal Coaptation n (%)	Nasal Obstruction Symptom Evaluation (NOSE)		
				Pre-op	Post-op	Δ
Septoplasty	Sainio  ,2019	101	-	-	-	-
Open septoplasty plus turbinoplasty	Sowerby⁵, 2013	8	-	12	2	10
Septoplasty	Tami  , 2010	24	24 (100%)	-	-	-
Septoplasty	Yildirim  , 2013	20*	-	-	-	5.7 ± 0.923
*Estimated number of patients $\Delta$ Change from preop to postop scores						

Table 4.2.1-1. ENTACT Septal Stapler Clinical Outcome Scores

Approximately 153 patients have undergone septoplasty using the ENTACT Septal Stapler in four studies Sowerby et al. conducted a prospective randomized study and reported a significant decrease in the mean operation time in the ENTACT Septal Stapler group compared to the quilting sutures group (28 ± 6 minutes vs. 43 ± 13 minutes respectively; p=0.014). The mean time for septal closure was also reported to be significantly lower in the ENTACT Septal Stapler group than the quilting suture group (35 ± 22 seconds vs. 420 ± 70 seconds; p<0.001). In a prospective case series conducted by Tami et al. the amount of time taken to apply staples from the ENTACT Septal Stapler was reported to be <60 seconds. Sainio et al. conducted a retrospective comparative study comparing ENTACT Septal Stapler to the non-stapler group where silicone splints, tamponade, or sutures were used during septoplasty.

This document contains information that is confidential and proprietary to Smith + Nephew PLC and Smith + Nephew, Inc. and is intended for use only by Smith + Nephew and its manufacturer. It shall not be reproduced or copied in whole or in part, nor shall the contents be disclosed by any means without prior written permission from Smith + Nephew, nor shall anyone make any use of it that is contrary to the expressed or implied wishes of Smith + Nephew.

Study Protocol	>{ smith&nephew
A prospective, multi-center, single arm PMCF study to evaluate	Number:
the safety and performance of ENTACT™ (Next Generation)	ENTACT.ENT.PRO.SEP.2019.05 Version: 2.0. 27Aug2020
Tesol Dable Septal Staple System for Septoplasty	Page: Page 22 of 94

ENTACT Stapler group and the non-stapler group (63.9 minutes vs. 64.3 minutes, respectively).

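### The edema and inflammation limits in Table 4.4.1-1 rest on pooled rates (2/153 and 5/153) that do not fit their source studies, so exceeding them would not show a difference from the predecessor device

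*Combined protocol and SAP*

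**What the plan says.** Section 4.2.2 of the protocol states: "Complications identified in the four clinical publications are reported in Table 4.2.2 -1". That table covers 153 stapler patients: 101 in a retrospective comparative study, 8 in a randomized trial against quilting sutures, 24 in a prospective case series, and an estimated 20 in a prospective comparative study. It shows edema only in the group of 8 (2 cases) and inflammation only in the series of 24 (5 cases). The other three rows carry a dash for each event.

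The text of Section 4.2.2 gives the detail. The randomized trial "observed mild edema in 2 patients in both the groups at a 3 week follow up"; in the case series, "mild inflammation was reported at a 1 week follow up in 21% of the patients in whom ENTACT Septal Stapler was used". It adds: "Expected rates of edema or inflammation following septoplasty were not discussed in the four publications identified".

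Table 4.4.1-1 nevertheless uses 2/153 (1.31%) and 5/153 (3.27%) as the literature rates. It allows at most 2/40 for edema and, for inflammation, "4/40 10% (95% CI 2.8% to 23.7"%). The column heading presents a count within the limit as showing no significant difference from the literature. The note below the table says "Actual study adverse events occurrences will be reviewed under" Sections 10.5 and 12 and compared with the limits. Neither of those sections mentions the limits.

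**The concern.** A pooled rate is a fair yardstick only if the pooled studies could plausibly share one rate. For edema and inflammation, every case comes from one small study, and about 80% to 95% of the denominator comes from studies showing none. Dividing by 153 turns a reported 21% into 3.27%, and 2 in 8 into 1.31%. The ceilings of 2 and 4 inherit those low figures.

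What is at stake is how the safety result is read. The study is meant to supply post-market evidence for CE marking, and the table attaches a statement about statistical difference to each count. Five inflammation cases in 40 (12.5%) would fall outside the limit, although the only study showing inflammation reported a higher rate. In the other direction, if sites treat mild reactions as normal healing and do not record them, the limits could be met without counting what the literature counted. In neither case do these two rows separate the new stapler from the old.

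**Working it through.** **Inputs.** Counts and group sizes: Table 4.2.2-1 and Section 4.2.2. Limits and N = 40: Table 4.4.1-1 and its note. Two-sided 95% level: Section 10.1.

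**1. Reproduce the plan's limits.** Rule: the largest k whose Clopper-Pearson lower bound for k/40 is at or below the literature rate. The lower bounds are 0.61% (k = 2), 1.57% (3), 2.79% (4) and 4.19% (5).
- Perforation and edema, 2/153 = 1.31%: limit 2.
- Hematoma, 1/153 = 0.65%: limit 2.
- Inflammation, 5/153 = 3.27%: limit 4.
- Infection, 6/153 = 3.92%: limit 4.

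All five match the table. So do the intervals: 0.61% to 16.92% for 2/40 and 2.79% to 23.66% for 4/40. A two-sample Fisher test would give 3, 2, 3, 4, 5, so that was not the method. The arithmetic is right; the question is the input rate.

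**2. Could one rate hold for all 153 patients?** Chance that all cases fall in the named study:
- Edema: C(8,2)/C(153,2) = 28/11,628 = 0.0024.
- Inflammation: C(24,5)/C(153,5) = 42,504/654,045,930 = 0.000065.

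**3. Read counts just over the limit against the source studies.**
- 5/40 = 12.5% (exact 95% CI 4.19% to 26.8%). The lower bound exceeds 3.27%, so the rule flags it. Yet 12.5% is below 5/24 = 20.8%, and the interval contains 20.8%.
- 3/40 = 7.5% (1.57% to 20.39%). It is flagged because 1.57% exceeds 1.31%, yet 7.5% is below 2/8 = 25%.

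**4. Chance of exceeding the limit**, X ~ Binomial(40, p), all mild cases recorded:

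| Rate assumed (edema; inflammation) | Edema, P(X ≥ 3) | Inflammation, P(X ≥ 5) |
|---|---|---|
| Pooled: 2/153; 5/153 | 1.5% | 1.0% |
| Lower exact 95% bounds of source rates: 3.2%; 7.1% | 13% | 15% |
| Three prospective studies (8 + 24 + 20): 2/52; 5/52 | 20% | 34% |
| Two source studies (8 + 24): 2/32; 5/32 | 46% | 77% |
| Source-study point estimates: 2/8; 5/24 | 99.9% | 94% |

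The exact 95% CIs of the source rates are 3.2% to 65.1% for 2/8 and 7.1% to 42.2% for 5/24. The expected counts at the point estimates are 40 × 2/8 = 10 and 40 × 5/24 = 8.3.

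**5. Sensitivity to recording**, starting from the source-study rates. If half of mild cases are recorded: edema 89%, inflammation 41%. If a quarter: 46% and 5.5%.

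**6. Can the limits be recalculated?** The plan's own rule applied to 2/8 and 5/24 gives 16/40 and 14/40, too loose to be useful. The edema and inflammation described in the literature were mild, so the described moderate or severe count is 0/153. The rule would then give 0/40, because the lower bound for 1/40 is 0.06%. The literature therefore supports neither a usable limit for all grades nor ceilings of 2 and 4 for the higher grades.

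**The case against.** **The dashes may be true zeros.** Table 4.2-1 has its own marker for unreported data, and Table 4.2.2-1 does not use it. The 101-patient study's 9.9% complication rate is about 10 patients. The table lists 1 + 1 + 6 = 8, and the text adds bleeding and fever, which leaves little room for edema or inflammation. On the other side, in Table 4.2.1-1 (introduced with "Improvement in clinical outcome scores with the ENTACT Septal Stapler are reported in") a dash marks outcomes that a study did not report. A reader might infer that the dashes mean not assessed; the documents do not settle it. The point does not need that reading, because the clustering in step 2 counts against a common rate either way. For edema the evidence is thinner, with only two cases: the chance that both fall in any one of the three smaller groups is (28 + 190 + 276)/11,628 = 4.2%. Even so, both in the group of 8 is the least likely of all placements.

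**The source studies are not clean measures of the current predecessor.** Both involved 2009 staplers with reported jamming or specification failures, before the 2010 and 2012 changes. Edema occurred with sutures too, after open septoplasty with turbinoplasty. This stands. It is why the chances above describe a device equal to the source studies, and why 2/8 and 5/24 are only imprecise references.

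**Mild reactions may not be recorded.** Section 4.4 says: "When implanted, the ENTACT Staple may elicit a minimal tissue reaction characteristic of foreign body response to a substance". Section 12.1.1 stresses whether an event is an untoward medical occurrence, and the nasal examination asks only about significant tissue reaction. This stands as well; full recording is an assumption, and step 5 shows its effect.

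**The limits carry no formal consequence.** A reader might infer that a breach would fail the study, stop it, or oblige the sponsor to report that the device causes significantly more events. The documents do not say so. The limits are not an endpoint, a success criterion or a stopping rule, and Section 10.5 leaves further safety summaries to a SAP whose text is not in the document reviewed. Tight limits also err toward more scrutiny. What remains is that the column heading attaches a statement about significance to thresholds that cannot support it.

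**Conclusion.** For edema and inflammation, 2/153 and 5/153 are not valid reference rates, and a count above 2 or 4 would not show a difference from the predecessor. The true chance of exceeding a limit cannot be pinned down. It is 13% (edema) and 15% (inflammation) at the lower exact bounds of the source rates, 20% and 34% at the prospective-study rates, and 99.9% and 94% at the point estimates, against 1.5% and 1.0% as the table implies. All of these assume that mild cases are recorded and that 40 subjects are treated.

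It is tempting to conclude that a breach is nearly certain. That would treat two very small studies of early devices as exact, which their confidence intervals do not allow. The perforation, hematoma and infection rows are not challenged. This is a correctable weakness in a stated threshold; it does not affect the primary analysis.

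**What to change.** For edema and inflammation only:

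1. Withdraw the limits of 2/40 and 4/40 as evidence of no significant difference from the literature.
2. In Table 4.4.1-1, show the source-study rates instead: 2/8 (exact 95% CI 3.2% to 65.1%) and 5/24 (7.1% to 42.2%). State that both are imprecise.
3. Add to Section 10.5 that the number of safety-population subjects with each event will be reported by severity (Section 12.1.5 grades) and by visit, with an exact 95% CI beside those rates.

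Keep the limits for perforation, hematoma and infection. Do not move the ceilings of 2 and 4 to moderate or severe events; step 6 shows that no literature in the protocol supports them.

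**Cost.** These two rows lose a numeric ceiling, although the events are still recorded and reported. The table sits in the protocol, so the change needs an amendment with signatory and IRB approval under Section 15. Since version 2.0 added the limits in an update requested by the notified body, some further discussion with that body is likely. No extra patients or visits are needed.
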